#### 9.4.2. Recording Adverse Events

A "pre-existing" condition is one that is present before study drug dosing and is reported as part of the subject's medical history. Pre-existing conditions should be reported as an adverse event only if the frequency, intensity, or character of the pre-existing condition worsens during the course of the study.

Subjects should be instructed to report all potential adverse events to the Investigator and should be queried in a nonleading manner, without specific prompting (e.g., "How are you feeling?"). The site study staff should assess emerging symptoms of dissociative reaction similar to those caused by *N*-methyl-D-aspartate antagonists, including memory impairment, disturbance in time, body or environmental perception, stilted speech, emotional withdrawal, impaired coordination, motor retardation, bizarre reasoning or illusory experiences in any sensory perception, or confused state; such symptoms may be captured as adverse events.

To avoid vague, ambiguous, or colloquial expressions, all adverse events should be recorded in standard medical terminology rather than in the subject's own words. Each adverse event will also be described in terms of duration (start and stop date), severity, relationship to study drug, action(s) taken, and outcome. Diagnoses (rather than symptoms) should be recorded wherever possible.

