The subject will be reminded not to exceed 2 g/day (one to two 500 mg tablets every 6 hours as needed up to 4 tablets total) for DPN related pain. Pain diary compliance will be reviewed by the study staff, and reporting instructions will be reinforced. Adverse events will be assessed by asking subjects a nonleading question. Misuse and abuse-related events will be assessed using the Misuse, Abuse, and Diversion Drug Event Reporting System® (MADDERS® [Analgesic Solutions, Wayland, MA]). Use of concomitant

medications will be documented.

The subject will be asked to complete the printed copy of the S-STS given to them at their Baseline Visit while communicating with the site staff. The staff will review the subject's answers to the S-STS and recommend corrections, only where the form has been completed incorrectly. The completed S- STS source document will be mailed back to the clinic or returned at the next study visit to be filed in the subject's chart and entered into the eCRF system. A subject may be asked to return to the clinic, per Investigator discretion, for additional study specific training or examination. Any unscheduled return to the clinic visit should be entered as an Unscheduled Visit in the eCRF and IRT systems.

Subjects will be instructed to continue entering their average pain intensity, worst pain intensity, average pain upon walking, and rescue medication use over the past 24 hours into their study-issued handheld devices every night, and to complete the DSIS and confirm they have taken their study drug in the past 24 hours via their study-issued handheld device every morning upon awakening. Subjects will be reminded of appropriate expectations around their participation in a clinical study and the importance of consistently and accurately reporting their pain throughout the study. APR®/PRR® training via the aLearn® portal is optional per investigator discretion for Week 2/Visit 3.

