### 9.3.6. Sheehan-Suicidality Tracking Scale

The standard version of the S-STS [Sheehan 2014] is a 16-item scale that assesses the seriousness of suicidality phenomena on a Likert-type scale (0 to 4) ranging from 0 = not at all to 4 = extremely. It also assesses the frequency of key phenomena and the overall time spent in suicidality. The standard version is available in identical clinician- and subject-rated formats.

The S-STS accommodates a wide range of time frames. In clinical studies, the frequently used variants are "in the past week," "in the past month," "since the last visit," "lifetime look back," and "in the past day".

Suicidality identified after baseline will be recorded as an adverse event.

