### 9.4. Safety and Pharmacovigilance

#### 9.4.1. Adverse Events – Relationship to Study Drug

An adverse event is any untoward, undesired, unplanned clinical event in the form of signs, symptoms, disease, or laboratory or physiological observations occurring in a human being participating in a clinical study with an Aptinyx study drug, regardless of causal relationship.

Laboratory abnormalities are not considered adverse events unless they are associated with clinical signs or symptoms or require medical intervention. However, a laboratory abnormality (e.g., a clinically significant change detected on clinical chemistry, hematology, or urinalysis results) that is independent from the underlying medical condition and that requires medical or surgical intervention, or leads to study drug interruption or discontinuation, must be considered an adverse event.

The causality of each AE should be assessed and classified by the Investigator as "related" or "not related." An adverse event is considered related if there is a reasonable possibility that the event may have been caused by the study drug under investigation (i.e., there are facts, evidence, or arguments to suggest possible causation). There is also a timely relationship to the administration of the investigational drug and the event follows a known pattern of response for which no alternative cause is present.

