### 9.4.3. Reporting Adverse Events

All adverse events must be documented, evaluated, and reported in the source documents and eCRF. Adverse events will be collected from the time of study drug administration through the last day of the subject's participation in the study. Follow-up of AEs must be conducted in accordance with the investigative site's normal practice. Ongoing adverse events should be followed to a satisfactory resolution in the Investigator's opinion. Subjects should be instructed to report all adverse events to the Investigator. In addition, the Investigator should seek to elicit any clinical or objective reactions by specific questioning (e.g., "How have you been feeling?") and as appropriate by examination. Information on all adverse events should be recorded on the eCRF. All clearly related signs, symptoms, and results of diagnostic procedures performed in relation to an adverse event should be grouped together and recorded as a single diagnosis.

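### Protocol 9.4.2 tells staff to look for dissociative symptoms but leaves recording them as adverse events optional, which is inconsistent with 9.4.1 and 9.4.3 and could understate their rates

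*Protocol*

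**What the plan says.** Protocol 9.4.2 gives an active instruction: "The site study staff should assess emerging symptoms of dissociative reaction similar to those caused by" NMDA antagonists. It lists examples such as memory impairment, altered perception, impaired coordination and confusion, and closes with "such symptoms may be captured as adverse events". It gives no criterion for when a symptom is or is not captured.

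The general rules are firmer. Protocol 9.4.1 states: "An adverse event is any untoward, undesired, unplanned clinical event in the form of signs, symptoms, disease, or laboratory or physiological observations", whatever the cause. Protocol 9.4.3 states: "All adverse events must be documented, evaluated, and reported in the source documents and eCRF". Two other safety topics with their own sections are also mandatory. For the suicidality scale, 9.3.6 says "Suicidality identified after baseline will be recorded as an adverse event", and 9.3.7 uses equivalent wording for misuse and abuse events.

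On elicitation, 9.4.2 says subjects "should be queried in a nonleading manner, without specific prompting", and the visit text agrees: "Adverse events will be assessed by asking subjects a nonleading question" (for example Synopsis, Week 2/Visit 3). Protocol 9.4.3 adds that "the Investigator should seek to elicit any clinical or objective reactions by specific questioning", and by examination where appropriate.

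SAP 6.12.1 tabulates treatment-emergent AEs (TEAEs) by system organ class, preferred term and maximum severity. It defines no grouping for dissociative symptoms.

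**The concern.** Dissociation is a safety topic the protocol names itself, yet its recording wording is weaker than that for suicidality or misuse. A specific permissive sentence beside a general mandatory one can be read either way. Some of the up to 37 sites (Protocol 6.1) may treat it as discretion not to record.

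Nothing else in the schedule fills the gap. Table 3 contains no dissociation scale: the S-STS covers suicidality and MADDERS covers misuse. Under 9.3.3, the comprehensive neurological examination, including mental status, is specified for Visit 1, while Week 12 has only a brief physical examination. The first scheduled post-dose contact, at Week 2, is by telephone or video.

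Safety and tolerability is a primary objective (Protocol 5.1), and safety summaries are descriptive only (12.7), so the recorded counts are themselves the result. A low recorded rate could not be told apart from low capture. The symptoms that are recorded may also scatter across preferred terms, so that no single row shows them.

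**Working it through.** **Text comparison**

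| Topic | Section | Recording rule |
|---|---|---|
| Any untoward sign or symptom | 9.4.1 with 9.4.3 | must |
| Suicidality after baseline | 9.3.6 | will |
| Misuse and abuse events | 9.3.7 | will |
| Dissociative symptoms | 9.4.2 | may |

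Only the last row is permissive, and it concerns symptoms that already fall under the first row. The defect is an inconsistency between sections.

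**Arm size.** SAP 4 gives a difference of 0.73, SD 1.7, two-sided alpha 0.05, power 80% and 15% drop-out. SAP 5 gives 1:1 allocation.

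- n per arm = 2 × (1.960 + 0.842)² × 1.7² / 0.73² = 85.1, rounded up to 86.
- 86 / 0.85 = 101.2, rounded up to 102 per arm, or 204 in total. This matches the plan.
- 204 / 37 sites is about 5.5 subjects per site.

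**Illustration of under-capture.** The documents give neither a dissociation rate nor a capture rate, so every rate below is assumed. Let true rates be 5% (active) and 1% (placebo), and let s be the share of cases recorded, equal in both arms. Expected active cases = 102 × 0.05 × s. Risk difference = s × (5% − 1%). Risk ratio = 5s/1s = 5. The last column is the binomial probability for n = 102 and p = 0.05s.

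| s | Expected active cases | Expected placebo cases | Risk difference | Risk ratio | P(at least 3 active cases recorded) |
|---|---|---|---|---|---|
| 100% | 5.1 | 1.0 | 4.0 points | 5 | 89% |
| 75% | 3.8 | 0.8 | 3.0 points | 5 | 74% |
| 50% | 2.6 | 0.5 | 2.0 points | 5 | 47% |
| 25% | 1.3 | 0.3 | 1.0 point | 5 | 14% |

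With assumed true rates of 10% vs 2%, the expected active cases are 10.2, 7.7, 5.1 and 2.6, and the last column reads 99.8%, 98.5%, 89% and 47%.

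**Could site practice bias the arm comparison?** Assume a true rate of 5% in both arms, with some sites capturing 90% and others 30%.

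- Each arm split evenly between the two kinds of site: capture is 0.5 × 0.9 + 0.5 × 0.3 = 0.60 in each arm. The recorded rate is 3.0% in both, ratio 1.00.
- One arm 60/40 and the other 40/60: capture is 0.66 vs 0.54. Recorded rates are 3.3% vs 2.7%, ratio 1.22.

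A spurious arm difference therefore needs the arms to be unbalanced across site types.

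**The case against.** **Recording is already compulsory.** A site that sees a dissociative reaction and records nothing would breach 9.4.1 and 9.4.3. This stands as far as it goes: a reader might infer that 9.4.2 creates a free-standing exemption, and it does not. The specific sentence still invites that reading and should be brought into line.

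***May* has a sensible meaning.** Under 9.4.2, pre-existing conditions are AEs only if they worsen, and diagnoses are preferred to symptoms. Under 9.4.3, related signs and symptoms go under one diagnosis. Not every observed symptom is therefore its own AE. This stands, and it rules out a blanket *must*.

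**The elicitation rules are not opposites.** A reader might infer that 9.4.2 and 9.4.3 contradict each other outright. But 9.4.3 is framed as an addition, and its sample question, like the one in 9.4.2, simply asks how the subject feels. The label of specific questioning is loose and needs reconciling, no more.

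**The arm comparison is largely protected.** A reader might infer that a low rate on NYX-2925 could be an arm-specific artefact of site practice. Subjects, study personnel and the sponsor are blinded (Protocol 8.1), so no route to differential recording is stated. The available text does not say whether randomization is stratified by site, so chance imbalance cannot be excluded, but nothing points to it.

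**Dissociation is not established for this drug.** Protocol 4 describes NYX-2925 as a co-agonist at a site distinct from the agonists and antagonists studied to date, and its list of commonest TEAEs has no dissociative term. Protocol 6.3 reports no AE difference from placebo in the first Phase 2 study. Calling it a class effect of this product would go beyond the text. The case for recording rests on the protocol's own choice to single these symptoms out.

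**A grouped row is optional.** SAP 6.12.1 already tabulates every preferred term and lists every AE, and SAP 6 allows further tables. But a grouping chosen after the data are seen carries less weight than one fixed in advance.

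**Conclusion.** The concern holds as an inconsistency worth correcting. The permissive wording in 9.4.2 conflicts with the mandatory rules around it, and no other scheduled measure or planned summary compensates. The exposure is to absolute rates and the risk difference. At an assumed 5% vs 1%, 50% capture halves the difference from 4 to 2 points and cuts the chance of seeing at least three active-arm cases from 89% to 47%. The risk ratio is unaffected if capture is equal in the two arms, which blinding and randomization make the default expectation.

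The size rests wholly on assumed rates; only the arm size of 102 comes from the plan. No sample-size, power or efficacy result changes.

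**What to change.** 1. **Protocol 9.4.2:** state that any listed symptom that is new or worsened after the first dose must be recorded as an AE, subject to the existing rules on pre-existing conditions and on grouping related symptoms under one diagnosis.
2. **Protocol 9.4.2 and 9.4.3:** reconcile the specific-questioning phrase with the nonleading question used in 9.4.2 and at the visits, while keeping the active assessment that 9.4.2 asks of staff.
3. **SAP 6.12.1:** before unblinding, agree a list of preferred terms and pre-specify one grouped dissociative-symptom TEAE row by arm.

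The cost is a few sentences of protocol text, a note to sites, a short term list to agree, one table row and slightly more AE entries. The protocol change helps only follow-up still to come. The SAP row can be added at any time before unblinding, but it cannot recover events that were never recorded.

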### 9.4.3. Reporting Adverse Events

All adverse events must be documented, evaluated, and reported in the source documents and eCRF. Adverse events will be collected from the time of study drug administration through the last day of the subject's participation in the study. Follow-up of AEs must be conducted in accordance with the investigative site's normal practice. Ongoing adverse events should be followed to a satisfactory resolution in the Investigator's opinion. Subjects should be instructed to report all adverse events to the Investigator. In addition, the Investigator should seek to elicit any clinical or objective reactions by specific questioning (e.g., "How have you been feeling?") and as appropriate by examination. Information on all adverse events should be recorded on the eCRF. All clearly related signs, symptoms, and results of diagnostic procedures performed in relation to an adverse event should be grouped together and recorded as a single diagnosis.

### 9.4.3.1. Severity of Adverse Events

All adverse events will be assessed for severity, using the following general grading scale:

- Mild: Transient or mild discomfort (<48 hours); no medical intervention/therapy required.
- Moderate: Mild to moderate limitation in activity some assistance may be needed; no or minimal medical intervention/therapy required.
- Severe: Marked limitation in activity, some assistance usually required; medical intervention/therapy, required hospitalization possible.
- Life threatening: Extreme limitation in activity, significant assistance required; significant medical intervention/therapy required, hospitalization, or hospice care probable.

When changes in the severity of an adverse event occur more frequently than once a day, the maximum severity for the experience that day should be noted. If the severity category changes over a number of days, then those changes should be recorded separately (with distinct onset dates).

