6.3.4 Descriptive Statistics

Continuous variables will be summarized by the number of non-missing observations, mean, median, standard deviation, and minimum and maximum.

Categorical variables will be summarized by presenting the frequency and percent. Percentages will be based on the number of non-missing observations or the subject population unless otherwise specified. For each variable, all categories will be shown. Zero frequencies (but not the percent) within a category will be presented.

Incidences of adverse events, medical history and concomitant medications will be reported at the subject level. Subjects can only be counted once within each PT and SOC under the highest severity and most related. Percentages will be calculated using the number of subjects in the treatment group for the Safety Population.

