6.11.3 Other Efficacy Endpoints

6.12.1 Adverse Events

Adverse events will be collected from the time of study drug administration through the last day of the subject's participation in the study.

A treatment emergent adverse event (TEAE) is defined as:

- Any AE that has an onset on or after the first dose of study drug, through the last day of the subject's participation in the study
- Any pre-existing AE that has worsened in severity on or after the first dose of study drug, through the last day of the subject's participation in the study

A treatment-related AE is defined as an AE classified by the Investigator as 'Related' to the study drug. If an AE has missing relationship it is assumed to be related to the study drug for analysis purposes.

Maximum severity (Life threatening) will be assumed for an AE with missing severity.

An overall summary table of AE incidence (number and percent of subjects) and number of events, will be presented by treatment group and overall, for the following categories:

- Any TEAE
- Treatment-Related TEAEs
- Serious TEAEs
- Serious Treatment-Related TEAEs
- TEAEs Leading to Study Drug Discontinuation
- TEAEs Leading to Early Withdrawal
- TEAEs Leading to Death

Summaries of TEAE incidence and number of events by SOC and PT will be presented by treatment group and overall, for the following:

- TEAEs
- Treatment-related TEAEs
- Serious TEAEs
- Serious Treatment-Related TEAEs
- TEAEs Leading to Study Drug Discontinuation
- TEAEs by Maximum Severity, (incidence only)

• Treatment-Related TEAEs by Maximum Severity, (incidence only)

The following listings of AEs will be presented in Section 14.3.2 of the CSR:

- Serious AEs
- AEs Leading to Early Withdrawal
- AEs Leading to Death

AE tabulations will be presented by SOC and PT in descending overall frequency of AE incidence and then alphabetically for ties.

All reported AEs will be listed in Appendix 16.2.7 of the CSR.

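### Adverse events split at each severity change are not rejoined before the SAP counts events, so the event-count columns can overcount

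*Protocol*

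**What the plan says.** **Recording.** Protocol 9.4.3.1 distinguishes two situations. Where severity changes more often than once a day, "the maximum severity for the experience that day should be noted", so no extra entry arises. Where it changes over a longer span, the rule is: "If the severity category changes over a number of days, then those changes should be recorded separately (with distinct onset dates". The text covers changes in either direction.

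**Grouping.** Protocol 9.4.3 says that related signs, symptoms and diagnostic results "should be grouped together and recorded as a single diagnosis".

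**Counting.** SAP 6.12.1 plans, across its overall categories, "An overall summary table of AE incidence (number and percent of subjects) and number of events". It continues: "Summaries of TEAE incidence and number of events by SOC and PT will be presented by treatment group and overall". Five of the tables listed under that sentence carry event counts: all TEAEs, treatment-related, serious, serious treatment-related, and those leading to study drug discontinuation. The severity tables do not: "TEAEs by Maximum Severity, (incidence only".

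**De-duplication.** SAP 6.3.4 states: "Subjects can only be counted once within each PT and SOC under the highest severity and most related". Protocol 12.7.1 has the same subject-level rule and plans subject counts and percentages only. Event counts are an addition in the SAP, and SAP section 9 does not list them as a change.

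**Treatment emergence.** The first criterion in SAP 6.12.1 depends only on onset at or after first dose. The second, for events already present, requires worsening. Protocol 12.7.1 likewise requires a rise in severity for an event that began before dosing.

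**The concern.** The recording rule and the counting rule do not fit together. The first turns one continuous adverse event into several dated entries. The second reports how many events occurred, and nothing between the two says that the entries must be rejoined. Read plainly, a long event of fluctuating grade adds more to the event columns than a short one of stable grade, although each is one event in one subject.

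The same splitting also touches the TEAE definition. A post-dose onset date on a continuation entry can satisfy the onset-based criterion even when the change was an improvement. What is at stake is the accuracy of descriptive safety columns and, in one rare situation, whether a subject appears in the serious TEAE tables at all.

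**Working it through.** Neither document states a figure for this point, so there is nothing to reproduce. The check sets the rules side by side and then illustrates the size.

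**1. Does any rule rejoin the entries?**
- The within-day rule in Protocol 9.4.3.1 takes the daily maximum. It does not reach changes across days.
- The grouping rule in Protocol 9.4.3 merges manifestations of one diagnosis. It says nothing about successive severity grades of that diagnosis.
- The outcome categories in Protocol 9.4.3.3 include none for an entry closed because its grade changed, so outcome does not mark a continuation.
- SAP 6.3.4 restricts how often a *subject* is counted. It leaves the event count open.
- The SAP does not define an event.

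**2. Worked case.** One subject has one headache that goes mild, moderate, mild over several days. It has two changes, so 1 + 2 = 3 entries. The subject count is 1. The event count is 3 if entries are counted, and 1 if they are rejoined.

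**3. Size, on assumed rates.** Let *s* be the share of true events whose grade changes and *c* the number of changes in each of those events. Then

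counted events = true events × (1 + *s* × *c*).

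Per 100 true events:

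| *s* (assumed) | *c* = 1 | *c* = 2 |
|---|---|---|
| 5% | 100 × 1.05 = 105 | 100 × 1.10 = 110 |
| 10% | 100 × 1.10 = 110 | 100 × 1.20 = 120 |
| 20% | 100 × 1.20 = 120 | 100 × 1.40 = 140 |
| 30% | 100 × 1.30 = 130 | 100 × 1.60 = 160 |

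After rejoining, every cell returns to 100.

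**4. The pre-dose serious event.** Protocol 9.5 collects serious events from consent, whereas Protocol 9.4.3 collects other adverse events only from study drug administration. Only a serious event can therefore have an entry before dosing. Suppose one is ongoing at first dose and its grade then falls. Protocol 9.4.3.1 gives the lower grade a new, post-dose onset. That entry meets the first TEAE criterion in SAP 6.12.1. It fails the second, because nothing worsened. The subject then enters the TEAE and serious TEAE tables, so here subject incidence changes as well.

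**The case against.** The strongest reply is that double counting is inferred. Protocol 9.4.3.1 says that changes are recorded separately; it does not say that each change is a new adverse event. The eCRF layout is not shown, and SAP 6.3.2 and 6.3.6 place the dataset specifications and table shells in separate documents. If severity entries sit under one identifier and events are counted by that identifier, the counts are right. This stands as a condition on the conclusion. It does not remove the point, because neither document states the link and the SAP should not leave the meaning of an event to the programmer.

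A reader might go further and infer three things that the documents do not support.

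- *That the main safety comparison is inflated.* It is not. Subject counts and percentages are protected by SAP 6.3.4 and Protocol 12.7.1, and the maximum-severity tables hold incidence only. Safety and tolerability is part of the primary objective, but the listed safety endpoints do not name event counts, and Protocol 12.7 rules out safety testing.
- *That the inflation favours or harms one arm.* The recording rule is the same in both arms of a double-blind trial, and nothing in the documents indicates that severity changes differ between them.
- *That the inflation has a known size.* Every percentage above is an assumption.

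The pre-dose case is also very rare. It needs a serious event after consent, still ongoing at randomization, in a subject who remains eligible at Visit 2, followed by improvement on treatment. The worsening requirement in SAP 6.12.1 and Protocol 12.7.1 shows what was intended. Even so, the first TEAE criterion as worded admits the case.

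**Conclusion.** The point holds as a gap in the SAP that affects descriptive event counts. Taken together, Protocol 9.4.3.1 and SAP 6.12.1 count one continuous adverse event of changing severity more than once, provided that the eCRF does not link the entries under one identifier. The size cannot be determined from the documents. With 5% to 30% of events changing grade once, the count would be 105 to 130 per 100 true events; with two changes each, 110 to 160. No endpoint, test or decision rule depends on these columns. Subject-level results are affected only through the pre-dose serious event that improves after dosing. This is a minor correction, worth making because the data needed for it are already collected.

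**What to change.** Add three rules to SAP 6.12.1, in this order.

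1. **Set TEAE status first.** An entry that continues an event begun before dosing is treatment-emergent only if its severity exceeds the pre-dose severity.
2. **Then collapse before counting events.** Join entries of the same subject and preferred term whose dates are contiguous, meaning that the next onset falls on the stop date of the previous entry or the day after. Keep the first treatment-emergent onset, the maximum severity, the most related causality, and any seriousness or study drug withdrawal.
3. **Keep recurrences apart.** Entries separated by a resolved interval count as separate events.

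The order matters: if entries were joined first, no later entry would be left on which to judge worsening. The contiguity condition matters too, since joining on subject and preferred term alone would merge true recurrences.

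Protocol 9.4.2 already has sites describe start and stop dates, severity, relationship and action taken, so no new data are needed. The cost is some SAP wording and one extra derivation step, with slightly lower event counts. Dropping the event columns would also remove the overcount, but rule 1 would still be needed.
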